- Post-baseline variant by clonal sequencing: a variant at a signature resistance-associated amino acid position that was not present in a subject by population sequencing at baseline, but that is detected in a post-baseline sample from that subject by clonal sequencing in at least 2 clones from that sample (among the subset of subjects for whom clonal sequencing is performed).
- Emerged variant by population sequencing: a post-baseline variant that is observed in samples from 2 or more subjects of the same HCV subgenotype by population sequencing.
- Linked variant by population sequencing: 2 or more signature resistance-associated or emerged amino acid variants identified within a target by population sequencing, and no mixture of amino acids is detected at either position.
- Linked variant by clonal sequencing: at least 2 clones from a given sample containing the same 2 or more signature resistance-associated amino acid variants by clonal sequencing.

Baseline samples will be sequenced by population sequencing for all subjects for whom samples are available. A listing by subject of all baseline variants relative to the appropriate prototypic reference sequence at signature resistance-associated amino acid positions will be provided for each DAA target (NS3, NS5A, and NS5B). In addition, a summary of the number and percentage of subjects with each baseline variant at a signature resistance-associated amino acid position within each target by HCV subgenotype out of the total number of baseline samples sequenced will also be provided.

The following analyses will be performed for subjects who do not achieve SVR₁₂ and have post-baseline resistance data available.

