Only samples with an HCV RNA level of \geq 1000 IU/mL will undergo sequence analysis in order to allow accurate assessment of products of amplification. Therefore if the HCV RNA level at the time of virologic failure (VF) or treatment discontinuation is $<$ 1000 IU/mL, the sample closest in time after the failure/discontinuation with an HCV RNA level \geq 1000 IU/mL will be used if available. Next generation sequencing (NGS) of a given target will be performed only if no variants are detected at signature amino acid positions by population sequencing in that sample. Included time points for analyses on subjects in the PVF and non-PVF population are: 1) time of virologic failure/treatment discontinuation or sample closest in time after failure/discontinuation with an HCV RNA level of \geq 1,000 IU/mL, 2) 24 weeks post-DAA treatment, provided that resistance-associated variants were detected by either population sequencing or NGS at the time of failure/discontinuation, and 3) 48 weeks post-DAA treatment, provided that resistance-associated variants were detected by either population sequencing or NGS at 24 weeks post-DAA treatment. For these samples, NGS will be performed on a given target only if no variants are detected at signature amino acid positions by population sequencing.

The regions of interest for population sequencing and NGS for all samples from subjects who do not achieve SVR₁₂ are those encoding complete NS3/4A, NS5A, and NS5B. The regions encoding NS3 amino acids 1 – 181, NS5A amino acids 1 – 215, and NS5B amino acids 1 – 591 will be sequenced for analysis of baseline samples from the SVR-achieving subjects. An appropriate prototypic reference sequence will be used for comparison with sequences from samples.

The following are considered signature amino acid positions in genotypes 2 and 3: 36, 43, 54, 55, 56, 80, 155, 156, 166 (GT3 only), 168 in NS3; 24, 28, 29, 30, 31, 32, 58, 92, 93 in NS5A; and 142, 159, 237, 282, 289, 320, 321 in NS5B.

The following definitions will be used in the resistance analyses:

- Baseline variant: a variant (by population sequencing) in a baseline sample determined by comparison of the amino acid sequence of the baseline sample to the appropriate prototypic reference amino acid sequence for a given DAA target (NS3, NS5A, or NS5B).
- Post-baseline variant by population sequencing: an amino acid variant in a post baseline time point sample that was not detected at baseline in the subject.

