- Variant at signature amino acid position: variant (relative to reference) present in a baseline or a post-baseline sample at a signature amino acid position (for NGS, detectable at 2% detection threshold).
- Emerged variant: a post-baseline variant that is observed in 2 or more subjects of the same subtype by population sequencing or NGS.
- Linked variant by population sequencing: 2 or more signature or emerged amino acid variants identified within a target by population sequencing, and no mixture of amino acids is detected at either position.

Analysis will be performed separately for each HCV subtype and study arms within each listing.

Analysis 1: The following analyses will be performed for all subjects:

- A listing of all baseline variants at signature amino acid positions for each DAA target (NS3, NS5A and NS5B) (ITT population).
- Listing of all baseline variants at non-signature amino acid positions for subjects in PVF population.
- The number and percentage of subjects with each baseline variant at a signature amino acid position within each target out of the total number of baseline samples that were sequenced will be provided (ITT population). This table includes prevalence of each baseline variant, and a summary of number of subjects with variants in NS3 only, in NS5A only, in NS5B only, any in NS3, any in NS5A, any in NS5B, any in NS3 or NS5A or NS5B, any in NS3 + NS5A, any in NS3 + NS5B, any in NS5A + NS5B, any in NS3 + NS5A + NS5B.

Analysis 2: The impact of baseline variants on treatment outcome will be assessed as follows: for each variant, the SVR₁₂ rate will be calculated for subjects with and without the variant and the 2 rates will be compared using Fisher's exact test. Subjects in the non-PVF population will be excluded from this analysis. Analysis will be grouped by (1) study Arm, (2) HCV subtype, (3) DAA target (NS3, NS5A or NS5B).

- Variants at signature amino acid positions (vs no variant at that position).
- Each variant at signature amino acid position (vs not that variant).
- Variants at non-signature amino acid positions (vs no variant at that positions).

Analysis 3: The following analyses will be performed for subjects in the PVF and non-PVF populations who have post-baseline resistance data available.

For analysis by population sequencing, the following tables will be provided:

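### SAP 10.7 makes NGS of failure samples depend on variants relative to the reference, so a polymorphism carried since baseline can switch NGS off and a selected minority variant in that target can be missed

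*SAP*

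**What the plan says.** SAP 10.7 states the sequencing rule twice. NGS of a target "will be performed only if no variants are detected at signature amino acid positions by population sequencing in that sample". After listing the time points (failure or discontinuation, and 24 and 48 weeks after treatment), it repeats: "For these samples, NGS will be performed on a given target only if no variants are detected at signature amino acid positions by population sequencing". This rule works target by target (NS3, NS5A, NS5B) and sample by sample.

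The same section defines a variant at a signature position as a "variant (relative to reference) present in a baseline or a post-baseline sample at a signature amino acid position", with the qualifier "for NGS, detectable at 2% detection threshold". The comparator is the reference sequence.

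Three other definitions matter:

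- At baseline: "Baseline variant: a variant (by population sequencing) in a baseline sample".
- A post-baseline variant is defined for population sequencing only. There is no NGS version.
- An emerged variant is "a post-baseline variant that is observed in 2 or more subjects of the same subtype by population sequencing or NGS".

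Protocol 8.1.4 has the same condition for clonal sequencing, with a shorter list of positions. It allows an exception for complex amino acid mixtures, which SAP 10.7 does not carry over.

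**The concern.** The purpose of a second, more sensitive assay is to look where population sequencing has not explained the failure. A polymorphism that was present before treatment and is still there at failure says nothing about what treatment selected. Under the rule as written it nevertheless counts as a detected variant and ends the search in that target. The assay's sensitivity at failure then depends on the subject's natural polymorphisms.

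Protocol 5.1.3 and SAP 4.2 both name the emergence and persistence of resistant variants as something the follow-up monitors. Few failures are expected, so a small number of unread targets would affect that description noticeably.

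**Working it through.** **Step 1: apply the rule to a case.** Suppose a subject has a polymorphism at NS5A position 30 at baseline and still has it at failure. Population sequencing of the failure sample shows a signature-position variant relative to the reference, so NS5A gets no NGS.

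- A variant selected at NS5A position 93, above 2% of the viral population but too rare for population sequencing, is not looked for.
- If the position 93 variant is common enough for population sequencing to see, it is reported. SAP 10.7 lists all post-baseline population-sequencing variants against the subject's own baseline, without condition.
- NS3 and NS5B in that sample are unaffected.

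Now take the Week 24 sample. If the position 93 variant was visible at failure but has since fallen below population-sequencing sensitivity, while position 30 remains, NGS is again skipped and position 93 looks lost. Week 48 sequencing depends on a resistance-associated variant being detected at Week 24. If the polymorphism is not counted as one, the miss carries forward. The SAP does not say whether it is.

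The documents do not give the population-sequencing threshold. That it is less sensitive than NGS at 2% is an assumption.

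**Step 2: count the signature positions.**

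| Target | Protocol 8.1.4 | SAP 10.7 |
|---|---|---|
| NS3 | 6 | 10 in GT3, 9 in GT2 (position 166 is GT3 only) |
| NS5A | 6 | 9 |
| NS5B | 1 | 7 |
| Total | 13 | 26 in GT3, 25 in GT2 |

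SAP 12.1 and 12.2 declare changes to the resistance plan, including added positions, so the longer list is not an inconsistency. Its effect is to make skipping more likely.

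**Step 3: chance that a baseline polymorphism switches NGS off.** No figure in the plan depends on this rule, so there is nothing to reproduce. With k positions, each polymorphic with probability q independently, the chance is 1 − (1 − q)^k. For NS5A at 5%, 1 − 0.95^9 = 37.0%.

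| Target | k | q = 1% | q = 2% | q = 5% | q = 10% |
|---|---|---|---|---|---|
| NS3 (GT3) | 10 | 9.6% | 18.3% | 40.1% | 65.1% |
| NS5A | 9 | 8.6% | 16.6% | 37.0% | 61.3% |
| NS5B | 7 | 6.8% | 13.2% | 30.2% | 52.2% |
| At least one target (GT3) | 26 | 23.0% | 40.9% | 73.6% | 93.5% |
| At least one target, protocol list | 13 | 12.2% | 23.1% | 48.7% | 74.6% |

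**Step 4: number of subjects.** At the 90% SVR12 rate that SAP 4.3 uses for illustration, 70 × 0.10 = 7 subjects do not respond. For NS5A, with q from 1% to 5%, the expected number with NGS skipped is 7 × 0.086 = 0.6 to 7 × 0.370 = 2.6. Seven is an upper count. It includes missing data and early discontinuation (SAP 10.1), and only samples with at least 1000 IU/mL are sequenced.

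**Step 5: the emerged-variant definition.** An NGS-only variant could be called emerged although the baseline definition uses population sequencing. The label needs two subjects of one subtype. If a fraction m of subjects carry the same unseen minority variant before treatment, and F failures of one subtype have NGS, the chance that at least two carry it is 1 − (1 − m)^F − F·m·(1 − m)^(F−1):

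| F | m = 5% | m = 10% | m = 20% |
|---|---|---|---|
| 1 | 0 | 0 | 0 |
| 2 | 0.3% | 1.0% | 4.0% |
| 5 | 2.3% | 8.2% | 26.3% |
| 7 | 4.4% | 15.0% | 42.3% |

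The values of m are assumed. F = 7 is an extreme case: every expected non-responder is of one subtype and has NGS.

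**The case against.** Using NGS only where population sequencing is uninformative is a sensible economy. Resistance is not a primary or secondary objective, the NGS output is a by-subject listing with no inference, and SAP 12.1 says the plan was aligned across the HCV program. All of that stands, and it limits the weight of the point. It does not answer why a pre-existing polymorphism should make a sample count as informative about emergence.

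A reader might infer something stronger: that the plan misses treatment-emergent resistance in general and also reports pre-existing variants as new. The documents do not support this.

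- Population sequencing against the subject's own baseline is unconditional, so only minority variants can be missed, and only in the target where NGS was skipped.
- In one target of one sample NGS is either skipped or run, so the two errors cannot occur together there.
- The SAP lists emerged variants only under population sequencing. Its single NGS listing shows all signature-position variants and makes no claim of emergence.
- SAP 10.7 refers to both sequencing methods for all samples from subjects without SVR12, so NGS of their baseline samples may be intended. The text leaves this open.
- The protocol does not call emergence by clonal sequencing. Its emerged variants are by population sequencing only. The mismatch there concerns a different category, the post-baseline variant by clonal sequencing, defined as one "that was not present in a subject by population sequencing at baseline, but that is detected in a post-baseline sample".

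It is also fair to say that the percentages in Step 3 measure how often NGS is skipped. A miss further requires a selected variant in that target, below population-sequencing sensitivity, and the documents give no basis for estimating that.

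**Conclusion.** The point holds as a limited, cheaply repaired weakness in a stated rule. Because the condition refers to the reference sequence, a baseline polymorphism alone can switch NGS off for a target at failure and at Post-Treatment Weeks 24 and 48. Nothing else in SAP 10.7 prevents this.

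The range of about 7% to 40% per target rests on three assumptions: a 1-5% prevalence per position, independence between positions, and the same prevalence among failures as among all subjects. It is not a rate of missed resistance.

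The loose definition of an emerged variant is secondary. It leaves room for a wrong label, but no planned table applies the label to an NGS-only finding.

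**What to change.** 1. Reword the trigger in SAP 10.7: NGS of a target is performed when population sequencing of that sample shows no signature-position variant that was absent from the subject's own baseline sequence. Skipping caused by a pre-existing polymorphism alone then falls to zero by construction.
2. Settle the emerged-variant definition in one of two ways. Either restrict it to population sequencing, or require the subject's baseline sample to be read by NGS at the same 2% threshold and otherwise list the variant as *baseline minority status unknown*. Under the second option, add a definition of a post-baseline variant by NGS.
3. State whether baseline samples from subjects without SVR12 receive NGS.

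The cost is SAP wording and NGS on a few more samples from a handful of failures. Resistance samples are already scheduled from Day 1, and archive plasma is kept (Protocol Tables 4 and 5, Section 5.3.1.1). No endpoint, sample size or clinical procedure changes.

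One limit remains. Where population sequencing already shows a new signature variant, minority variants elsewhere in that target still go unread. Running NGS on every sequenced failure sample would remove that limit at a higher assay cost.

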8.1.4 Resistance Analyses

The genes of interest for population sequencing in this study are those encoding full length NS3/4A, NS5A, and NS5B. For clonal sequencing, the DNA encoding NS3 amino acids 1 – 181, NS5A amino acids 1 – 215, and NS5B amino acids 280 – 591 will be sequenced. Amino acid positions where resistance-associated variants have been identified in vitro and/or in vivo in genotype 3 are 56, 80, 155, 156, 166, and 168 in NS3 for ABT-450; 28, 30, 31, 32, 58, and 93 in NS5A for ombitasvir; and 282 in NS5B for sofosbuvir.

Only samples with an HCV RNA level of \geq 1,000 IU/mL will undergo sequence analysis in order to allow accurate assessment of products of amplification. Therefore if the HCV RNA level at the time of virologic failure or treatment discontinuation is $<$ 1,000 IU/mL, the sample closest in time after the failure/discontinuation with an HCV RNA level \geq 1,000 IU/mL will be used. Included time points for analyses on samples from subjects who do not achieve SVR₁₂ are: 1) time of virologic failure/treatment discontinuation or sample closest in time after failure/discontinuation with an HCV RNA level of \geq 1,000 IU/mL, 2) 24 weeks post-DAA treatment, provided that resistance-associated variants were detected by either population or clonal sequencing at the time of failure/discontinuation, and 3) 48 weeks post-DAA treatment, provided that resistance-associated variants were detected by either population or clonal sequencing at 24 weeks post-DAA treatment. For these samples, clonal sequencing of a given target will be performed only if no variants are detected at signature resistance-associated amino acid positions by population sequencing. In addition, clonal sequencing may be performed if there is a complex mixture of amino acids at a signature resistance-associated position that cannot be resolved by population sequencing.

The following definitions will be used in the resistance analyses:

- Baseline variant: a variant (by population sequencing) in a baseline sample determined by comparison of the amino acid sequence of the baseline sample to the appropriate prototypic reference amino acid sequence for a given DAA target.
- Post-baseline variant by population sequencing: an amino acid variant detected by population sequencing in a post-baseline time point sample that was not detected by population sequencing at baseline in the subject.

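### After NS3 position 181 and NS5A position 215 only subjects without SVR12 have baseline sequence, so SAP 10.7 Analysis 2 cannot validly compare SVR12 by non-signature variant there

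*SAP*

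**What the plan says.** SAP 10.7 sets two sequencing regions.

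- For all samples from subjects who do not achieve SVR12, baseline included, the regions "are those encoding complete NS3/4A, NS5A, and NS5B".
- For responders a shorter set, namely NS3 up to position 181, NS5A up to 215 and NS5B up to 591, "will be sequenced for analysis of baseline samples from the SVR-achieving subjects".

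Analysis 2 in the same section takes each baseline variant, computes SVR12 with and without it, and "the 2 rates will be compared using Fisher's exact test". One of its three comparisons is "Variants at non-signature amino acid positions (vs no variant at that positions". Two further rules shape the tables: "Subjects in the non-PVF population will be excluded from this analysis" and "Analysis will be grouped by (1) study Arm, (2) HCV subtype, (3) DAA target (NS3, NS5A or NS5B".

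Analysis 2 does not confine the test to positions sequenced in both groups, and it does not say how a position without sequence is counted. The only denominator rule, based on the baseline samples actually sequenced, belongs to the signature-position table in Analysis 1.

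For background, Protocol 8.1.4 states: "The genes of interest for population sequencing in this study are those encoding full length NS3/4A, NS5A, and NS5B". It makes no split by outcome.

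**The concern.** The predictor (variant or no variant) is ascertained differently according to the outcome (SVR12 or not). At any position outside the responders' region, a variant can be found only in a failure. A programmer following the SAP could therefore produce a table in which an ordinary polymorphism appears to separate failures from responders, or a table that contains no responders at all. Neither says anything about whether the baseline variant affects response, which is the purpose of Analysis 2.

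**Working it through.** **Inputs.** Regions, test, exclusion and grouping: SAP 10.7. Arm sizes: about 10 in Arms A, B, C, D and F and about 20 in Arm E (SAP 4.2). Illustrative SVR12: 90% (SAP 4.3). The SAP gives no significance level or sidedness for Fisher's test; I assume two-sided 0.05. Variant prevalence is not given, so I show a range.

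**1. The plan's own figures.** The documents give no figure for the resistance test. The Wilson intervals in SAP 4.3 anchor arm size and response rate. The centre is (p + z²/2n)/(1 + z²/n) and the half-width is z√(p(1−p)/n + z²/4n²)/(1 + z²/n), with z = 1.96.
- n = 10, p = 0.9: 0.789 ± 0.193, or (59.6%, 98.2%).
- n = 20, p = 0.9: 0.836 ± 0.137, or (69.9%, 97.2%).

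Both agree with the SAP.

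**2. Which positions are affected.**

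| Target | Responders sequenced to | Highest signature position | Covered in failures only |
|---|---|---|---|
| NS3 | 181 | 168 | after 181 |
| NS5A | 215 | 93 | after 215 |
| NS5B | 591 | 321 | none, if 591 is the last residue |

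Every signature position is covered in both groups. So are non-signature positions within NS3 1–181 and NS5A 1–215. The documents do not say that NS5B ends at 591, though the protocol's clonal range for NS5B also stops there. NS4A is sequenced only in failures, but it is not a named target in Analysis 2, so it matters only if it is analysed.

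**3. Unsequenced treated as missing.** Only failures remain at the affected positions. SVR12 is 0% with the variant and 0% without it, and Fisher p = 1. The test is empty.

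**4. Unsequenced coded as no variant.** With f failures among n subjects, all carrying the variant, carriers have 0/f SVR12 and the others (n−f)/(n−f). For the cases below, two-sided p = 1/C(n, f).

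| n | f = 1 | f = 2 | f = 3 |
|---|---|---|---|
| 10 | 1/10 = 0.10 | 1/45 = 0.022 | 1/120 = 0.0083 |
| 20 | 1/20 = 0.050 | 1/190 = 0.0053 | 1/1140 = 0.0009 |

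A p-value below 0.05 therefore needs at least two failures in the same table.

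**5. False-positive rate under that coding.** Let the variant have prevalence q, unrelated to outcome. With two failures, p < 0.05 requires both to carry it, since one carrier gives p = 2/10 or 2/20. The rate per position is q²: 0.25 at q = 0.5, 0.81 at q = 0.9 and 1.0 at q = 1. When both groups have sequence at the position, exact enumeration (n = 10 or 20; 1 to 3 failures; q from 0.25 to 1) gives at most 0.019.

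**6. How often two failures occur.** P(≥2) = 1 − (1−π)ⁿ − nπ(1−π)ⁿ⁻¹.
- π = 0.10, every SVR12 failure counted: 0.26 for n = 10 and 0.61 for n = 20.
- π = 0.05, assuming half of failures are non-PVF and so excluded (ignoring the small loss of subjects): about 0.09 and 0.26.

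Grouping by subtype lowers these further whenever an arm contains more than one subtype.

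**The case against.** The strongest reply is that the SAP's general rules already steer away from the harmful coding. SAP 6.3 allows no imputation outside the HCV RNA endpoints. SAP 10.6 presents other endpoints as observed. SAP 10.7 defines a baseline variant by comparing the sample's sequence with a reference, so status at a position presupposes sequence there. On that reading the affected tests are uninformative rather than misleading. This largely stands, and it makes missing the better-supported reading. But none of these rules addresses partial sequence coverage in Analysis 2, and the reading they favour still leaves a planned test that cannot work.

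Three stronger inferences are tempting, and the documents do not support them.

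- *The plan will report false resistance associations.* That needs the less-supported coding, at least two virologic failures in one arm and subtype, and a variant common among them. With one failure, p is 0.10 or 0.050.
- *The whole non-signature comparison is invalid.* Positions inside the shared region are sequenced in both groups and can be compared.
- *The difference from the protocol is an error.* SAP 12.1 declares that the resistance plan was updated. Protocol 8.1.4 planned no test of baseline variants against SVR12, and its baseline summaries were confined to signature positions.

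It is also fair to say that the analysis is exploratory and that no decision rule depends on it.

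**Conclusion.** The point holds for non-signature positions after NS3 181 and after NS5A 215, and for NS4A if it is analysed. There the planned comparison has sequence from one outcome group only, so neither handling of the gaps gives a valid test. The likelier result is an empty table. The artefact, with p = 0.022 (2 of 10) or 0.0053 (2 of 20), depends on no-variant coding, on all failures carrying the variant, and on those failures being virologic and sharing an arm and subtype. The two-sided 0.05 level is also my assumption. The number of affected positions cannot be derived from the documents. Signature-position tests and the primary and secondary endpoints are untouched. Severity is low.

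**What to change.** Amend SAP 10.7, Analysis 2:

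- limit the non-signature comparison to NS3 1–181, NS5A 1–215 and NS5B 1–591 in all subjects;
- count a subject at a position only if sequence was obtained there, and show that denominator in the table;
- list failures' baseline variants outside that region descriptively, with no SVR12 comparison.

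Analysis 1 already lists non-signature baseline variants for the PVF population, so the third item adds little work. The cost is one or two sentences and a programming filter. No valid comparison is lost, because none is possible outside the shared region. Sequencing every baseline sample over the same region would also solve the problem, but it adds laboratory work.

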4.2 Design Diagram

This is a Phase 2, randomized, open-label, multicenter study evaluating the efficacy and safety of co-administration of ombitasvir/ABT-450/r with SOF with or without RBV administered for 12 weeks in HCV GT3 (with and without cirrhosis) and 8 and 6 weeks for GT2 (without cirrhosis) infected, treatment-naïve and treatment-experienced (previous pegIFN/RBV and/or SOF) adults. Approximately 70 subjects will be enrolled at approximately 8 sites globally.

[figure not shown]
Treatment Period and Post-Treatment Period

Approximately 20 GT3 subjects without cirrhosis meeting the eligibility criteria will be randomized 1:1 into Arm A and Arm B and treated as below:

- Arm A: ombitasvir/ABT-450/ritonavir 25/150/100 mg once daily (QD) and SOF 400 mg (QD) for 12 weeks;
- Arm B: ombitasvir/ABT-450/ritonavir 25/150/100 mg once daily (QD) and SOF 400 mg (QD) with RBV 1000 – 1200 mg divided twice daily (BID) per local label for 12 weeks.

Randomization to Arms A and B will be stratified by IL28B genotype (CC versus non-CC) and prior treatment status (treatment-naïve versus treatment-experienced).

Approximately 10 GT2 subjects meeting the eligibility criteria will be enrolled in to each of Arm C and Arm D and treated as described below. Arm D would be launched if no more than one subject who completes treatment in Arm C experiences relapse through PT Week 4.

Figure 1. Study Schematic

- Arm C: ombitasvir/ABT-450/ritonavir 25/150/100 mg once daily (QD) and SOF 400 mg (QD) with weight based RBV 1000 – 1200 mg BID per local label for 8 weeks;

- Arm D: ombitasvir/ABT-450/ritonavir 25/150/100 mg once daily (QD) and SOF 400 mg (QD) with weight based RBV 1000 – 1200 mg BID per local label for 6 weeks;

Approximately 20 subjects with genotype 3 HCV infection with compensated cirrhosis (a minimum of approximately 20% will be treatment-experienced) will be enrolled into Arm E:

- Arm E: ombitasvir/ABT-450/r 25 mg/150 mg/100 mg and SOF 400 mg QD with RBV 1000 – 1200 mg BID for 12 weeks

An additional 10 subjects with genotype 3 HCV infection without cirrhosis will be enrolled in open-label fashion into Arm F:

- Arm F: ombitasvir/ABT-450/r 25 mg/150 mg/100 mg and SOF 400 mg QD for 12 weeks

RBV dosing will be weight-based, either 1000 mg or 1200 mg daily divided BID per local label (e.g., < 75 kg = 1000 mg daily divided BID or ≥ 75 kg = 1200 mg daily divided BID).

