4.3 Sample Size

It is planned to enroll approximately 70 subjects into this study. With a sample size of 10 subjects per arm and an observed SVR₁₂ rate of 90%, the 2-sided 95% confidence

interval, using Wilson's score confidence interval, will be (59.6%, 98.2%); With a sample size of 20 subjects per arm and an observed SVR₁₂ rate of 90%, the 2-sided 95% confidence interval, using Wilson's score confidence interval, will be (69.9%, 97.2%). Subjects who do not have data at PT Week 12 (after performing the described imputation) count as failures for SVR₁₂ so no adjustment for dropout is applicable.

From the perspective of safety assessment, the probability that a given adverse event would not be observed among 70 subjects is shown in the second column of [Table 1](#) for various true population incidence rates. With 70 subjects, the probability is at least 99.9% to observe an adverse event with an incidence rate of 10% or higher.

Table 1. Probability of Not Observing an Adverse Event or Lab Abnormality with 70 Subjects for Various True Incidence Rates

True Incidence Rate	Probability of Not Observing
0.10	< 0.001
0.20	< 0.001
0.30	< 0.001
0.40	< 0.001
0.50	< 0.001

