10.2 Handling of Multiplicity

No multiplicity issue applicable in this study.

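### SAP 10.7 Analysis 2 tests baseline variants against SVR12 only within arm and subtype, where a 10-subject arm at 90% SVR12 usually cannot reach p < 0.05; an arm-stratified pooled test should be added

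*SAP*

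**What the plan says.** SAP 10.7, Analysis 2, sets out to assess whether baseline variants affect outcome. For each variant the SVR12 "rate will be calculated for subjects with and without the variant and the 2 rates will be compared", and the method is that "the 2 rates will be compared using Fisher's exact test".

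The layout is given as "Analysis will be grouped by (1) study Arm, (2) HCV subtype, (3) DAA target (NS3, NS5A or NS5B". A general rule placed before Analysis 1 reads "Analysis will be performed separately for each HCV subtype and study arms within each listing". Nothing in 10.7 pools or stratifies across arms.

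Three sets of comparisons are listed: any variant at a signature position, each individual variant at a signature position, and "Variants at non-signature amino acid positions (vs no variant at that positions". Non-responders outside the primary virologic failure population are left out of Analysis 2. No alpha is stated, and the tests are not labelled exploratory.

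SAP 4.2 gives the arm sizes. For the first two arms: "Approximately 20 GT3 subjects without cirrhosis meeting the eligibility criteria will be randomized 1:1 into Arm A and Arm B". Arms C, D and F also have about 10 subjects each, and Arm E about 20. SAP 4.3 illustrates precision "With a sample size of 10 subjects per arm and an observed SVR₁₂ rate of 90"%. SAP 10.2 states: "No multiplicity issue applicable in this study".

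**The concern.** Fisher's test conditions on the number of failures. In a very small arm with a high response rate there are too few failures for any split between carriers and non-carriers to give a small p-value. The test then carries no information about the variant.

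Analysis 2 is the only planned inferential look at baseline variants and outcome, and Protocol 5.6.1 lists development and persistence of resistance among the things the study should inform. As written, its likely output is a long set of non-significant p-values. A reader could take them as evidence that baseline variants do not matter, when in most 10-subject arms no data pattern could have shown otherwise.

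**Working it through.** **Inputs**
- Arm sizes (SAP 4.2): about 10 in A, B, C, D and F; about 20 in E.
- SVR12 of 90% (SAP 4.3): an observed rate chosen to show interval width, varied below.
- Test (SAP 10.7): Fisher's exact test within arm and subtype.
- Threshold: two-sided p < 0.05. This is an assumption, in line with the 2-sided 95% intervals used elsewhere in the SAP.

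**Step 1: the plan's own figure.** The Wilson interval is [p + z²/2n ± z√(p(1−p)/n + z²/4n²)] / (1 + z²/n). For 9/10 it gives (59.6%, 98.2%) and for 18/20 it gives (69.9%, 97.2%). Both match SAP 4.3.

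**Step 2: smallest attainable p.** With f failures among n, the most extreme table has every failure carrying the variant and no responder carrying it. Its probability is 1/C(n, f).
- n = 10, f = 0: no comparison exists.
- n = 10, f = 1: 1/10 = 0.10.
- n = 10, f = 2: 1/45 = 0.022, and only if exactly 2 (or 8) subjects carry the variant and the split is perfect.
- n = 10, f = 3: 1/120 = 0.008.
- n = 20, f = 1: 1/20 = 0.05 exactly, which is not below 0.05.
- n = 20, f = 2: 1/190 = 0.005.

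So both arm sizes need at least two failures.

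**Step 3: how often that fails.** P(f ≤ 1) = sⁿ + n(1−s)sⁿ⁻¹, where s is the SVR12 rate. For n = 10 and s = 0.90: 0.349 + 0.387 = 0.736. For n = 20: 0.122 + 0.270 = 0.392.

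| SVR12 | n = 10 | n = 20 |
|---|---|---|
| 80% | 37.6% | 6.9% |
| 85% | 54.4% | 17.6% |
| 90% | 73.6% | 39.2% |
| 95% | 91.4% | 73.6% |

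Splitting by subtype makes it worse. At 90%, a subtype group of 8 cannot reach p < 0.05 in 81.3% of cases. A group of 5 never can, because its smallest possible p is 1/C(5, 2) = 0.10. These group sizes are illustrative; the documents do not forecast the subtype mix. Leaving out non-virologic non-responders can only lower the failure count further.

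**Step 4: power with and without pooling.** Assume 20% carriers, SVR12 60% in carriers and 97.5% in non-carriers (overall 0.2 × 60% + 0.8 × 97.5% = 90%), one subtype, unadjusted 0.05. The stratified test fixes the carrier and failure totals in each arm, sums the failing carriers over arms, and takes the two-sided p from the resulting sum of hypergeometric distributions.

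| Analysis | Power |
|---|---|
| Fisher, one 10-subject arm | about 7% |
| Fisher, Arm E (n = 20) | about 32% |
| Stratified exact, genotype 3 (A, B, E, F; n = 50) | about 76% |
| Stratified exact, genotype 2 (C, D; n = 20) | about 28% |

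An unstratified pooled Fisher test for genotype 3 gives about 82%, so stratifying costs roughly 6 points. If a single true signal had to clear 0.05/26, the strictest false-discovery-rate step over the 26 genotype 3 signature positions (10 in NS3, 9 in NS5A, 7 in NS5B), power would be about 32% for genotype 3. The same threshold would leave about 2% for genotype 2.

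**The case against.** **The rate and the threshold are not the plan's.** The 90% illustrates interval width and is not a design assumption; 0.05 is supplied here. This stands. At 80% SVR12 the unattainable share in a 10-subject arm is 37.6%, so the word usually holds at 85% and 90% but not at 80%. For Arm E, the Protocol Introduction reports lower response with cirrhosis, so its 39% may be too high.

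**Multiplicity.** A reader might infer from SAP 10.2 that a large unadjusted family will produce many false findings. Signature positions alone allow up to 26 × 4 + 25 × 2 = 154 position-level comparisons, before individual variants, subtypes and non-signature positions. The documents do not support that alarm. A comparison exists only where a position varies within the group. Moreover, under no effect, at 90% SVR12 and 20% carriers, a 10-subject arm gives p < 0.05 only about 0.2% of the time and Arm E under 1%. The discreteness that makes these tests uninformative also keeps false positives rare. SAP 10.2 is right for the primary and secondary endpoints, which are single-arm intervals; it merely overlooks the Fisher tests.

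**By-arm analysis is defensible.** Arms differ in ribavirin, cirrhosis and duration, and a variant might matter more in some than in others. SAP 12.2 records the presentation by subtype and arm as a deliberate update. This stands as a reason to keep by-arm results, but not as a reason to have nothing else.

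**The study is a pilot.** Protocol 5.6.1 describes it as pilot and exploratory, Protocol 8.1.4 plans no test of baseline variants against outcome, and the SVR12 rates are shown beside each test. This limits the harm. It does not make the tests informative.

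**Grouping may mean table layout only.** That is possible, but the general rule in SAP 10.7 on separate analysis by subtype and arm points the other way, and no pooled test is described.

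**Conclusion.** The point holds for power, not for false positives. At the SAP's illustrative 90% SVR12 and an assumed two-sided 0.05, about three in four 10-subject arms cannot yield p < 0.05 for any variant. For Arm E it is about two in five. A stratified pooled test would raise genotype 3 power from about 7% per 10-subject arm to about 76% in the scenario shown. The gain for genotype 2 is modest, at about 28%, and depends on Arm D opening, which SAP 4.2 makes conditional on relapse in Arm C.

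Three stronger readings are not supported. It is not true that no arm can reach significance: at 90%, some split could do so in 26.4% of 10-subject arms and 60.8% of the time in Arm E, although attainable is not the same as well powered. Nothing requires the by-arm results to be dropped. Nor is a false-discovery-rate adjustment required in a pilot study; it would take back much of the genotype 3 gain. The weakness is confined to the baseline-variant inference, and no SVR12, relapse or safety conclusion changes.

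The power figures rest on one assumed prevalence and effect, a single subtype and no adjustment.

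**What to change.** - In SAP 10.7 Analysis 2, add as the main comparison for signature positions an exact test of SVR12 with versus without the variant, stratified by arm and pooled within genotype and subtype (genotype 3: A, B, E, F; genotype 2: C, D).
- Keep the by-arm SVR12 counts with and without each variant beside it.
- State the alpha and sidedness, and describe these p-values as exploratory and unadjusted. Add that a non-significant by-arm result is not evidence of no effect. A false-discovery-rate adjustment is optional.
- Limit the statement in SAP 10.2 to the primary and secondary endpoints.

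Cost: SAP wording and one extra set of tables, with no new data and no design change. The downside is that the pooled test has most power when the variant effect is broadly common across arms that differ in ribavirin, cirrhosis and duration. Stratification handles different baseline response rates but not different variant effects, which is why the by-arm results stay.
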